4.9 Data Monitoring Committee or other review board

No Data Monitoring Committee or other review board will take place in the current study.

6 APPENDIX: SUPPORTING DOCUMENTATION

6.1 Appendix 1: Coding dictionaries

Medical history and adverse events (AEs) will be coded using the Medical Dictionary for Regulatory Activities (MedDRA).

Medications will be coded using the World Health Organization Drug Dictionary (WHO-DD). Medical procedures will not be coded.

6.2 Appendix 2: Disposition of study participants

The following summaries will be created.

Reasons for screen failures will be summarized using the ScS.

Disposition of participants screened table in ScS will also be created to summarize by region the number of sites, and provide information on the principal investigator name, dates of first participant in and last participant out as well as the number of screened/screen failure participants.

Disposition of analysis sets will be summarized in ScS and will state the number and percentage of participants in each of the following sets: (ES, SS, PK-PPS).

Disposition and discontinuation reasons output using ES will include the number and percentage of study participants who started, completed or discontinued the Intervention Period as well as the primary reason of discontinuation.

Discontinuation due to AEs output in SS will summarize the total number of study participants who discontinued the study due to AEs when AEs were serious and fatal, and or non-fatal.

A separate output in ES will be created to indicate the number of participants in each visit.

Listings of study participant disposition and study discontinuation, analysis set and study participants who did not meet study eligibility criteria will be provided.

6.3 Appendix 3: Baseline characteristics and demographics

6.3.1 Baseline characteristics and demographics

Participant demographics and baseline characteristics will be summarized (and listed in SS), using descriptive statistics as detailed in Section 4.1.

- Age (years), calculated as (date of informed consent – date of birth)/365.25
- Height (cm)
- Weight (kg)
- Body mass index (BMI) (kg/m^2) calculated as: $BMI = \frac{\text{Weight (kg)}}{(\text{Height (m)})^2}$ using the weight and height measurements obtained at screening.

Descriptive statistics for categorical variables (including counts and percentages) will be provided for:

- Gender (Male/Female/Unknown/Undifferentiated)
- Race (American Indian or Alaska native, Asian, Black, Native Hawaiian or other Pacific Islander, White, Other/Mixed)
- Ethnicity (Hispanic or Latino, Not Hispanic or Latino, Not Reported, Unknown)
- Age (<18, 18 - <65, 65 - <85 and ≥ 85 years).
- Geographic region (North America/Europe)
- Country
- BMI in kg/m^2 (<18.5, 18.5 - <25, 25 - <30, 30 - <35, 35 - <40, ≥ 40)
- BMI in kg/m^2 (tertile grouping)
- Weight in Kg (<43, 43 - <56, 56 - <77, 77 - <150, ≥ 150)
- MGFA Disease Class at Screening (Class I, IIa, IIb, IIIa, IIIb, Iva, IVb, V)
- Dose of previous Zilucoplan use prior to study entry (16.6, 23.0, 32.4 mg)
- MG0011 participant (yes, no)

Child-bearing potential will only be listed in ES.

6.4 Appendix 4: Protocol deviations

Important protocol deviations (IPDs) are deviations from the protocol which could potentially have a meaningful impact on the study conduct, on the primary analysis, key safety or PK outcomes for an individual participant. IPDs will be identified and documented prior to data base lock to confirm exclusion from analysis sets.

The number and percentage of participants with IPDs will be assessed in SS based on the following standard UCB categories:

- Inclusion criteria deviation
- Exclusion criteria deviation
- Withdrawal criteria deviation
- Prohibited concomitant medication use
- Incorrect treatment or dose
- Treatment non-compliance
- Procedural non-compliance

A participant might be included in more than one IPD category.

A listing of the important protocol deviations will be in ES.

6.5 Appendix 5: Medical history

Pre-existing conditions for participants entering the DV0013 from MG0011 will be captured from data of the parent study.

Medical History will be summarized as in absolute and relative frequency tables based on MedDRA SOC, HLT and preferred term (PT) terminology in SS. A participant will be counted only once for each HLT and SOC. The summary will present the results alphabetically by SOC, HLT within SOC, and within HLT, by decreasing frequency for the PT.

Medical History will be listed in SS; same stands for the procedures history. In these listings, the start/Stop dates of medical history conditions (or procedures) will be shown as they are originally recorded in the eCRF thus, not imputed.

6.6 Appendix 6: Prior/concomitant/follow-up medications

For MG0011 participants who have entered the DV0013 the following apply:

- Ongoing medications in MG0011 (may fall in the categories of prior/baseline/concomitant medications) will be rolled over from the parent study to DV0013.
- Past medications will be captured via the parent study based on treatment stop date (or imputed stop date if necessary).

For all study participants it is any medication taken at least once during the 30 days prior to the first dosing in DV0013 that will be entered in the summary outputs. Exception to this, is for Neisseria vaccination outputs that the complete Neisseria vaccination history will be summarized within participants in SS (parent study data will also be used to

display the Neisseria vaccination full history within participants entering the study from MG0011).

Definition of medication classification is given in the section that follows.

6.6.1 Prior/concomitant medications classification

Medications will be classified as follows based on imputed start and stop dates & times as outlined in Section 4.1.1.4.

- **Past** medications will include any medications that started and stopped before the first administration of ZLP-AI.
Of note, only past medications within the previous 30 days from screening will be considered in the table summaries or listings.
- **Prior** medications will include any medications that started before the first administration of ZLP-AI.
Of note, only prior medications used within the previous 30 days from screening will be considered in the table summaries or listings.
- **Baseline** medications will include any medications that started prior to dosing and continued after (classified as prior and concomitant medications).
- **Concomitant** medications will include any medications that have been taken at least once after the first use of ZLP-AI.
- **Concomitant Only** medications will include any medication that started the first use of ZLP-AI.

Table 6–1: Prior and Concomitant Medications

Medication Started	Medication finished	Classification
Before 1st self-injection with ZLP-AI	Before 1st self-injection with ZLP-AI	Past
Before 1st self-injection with ZLP-AI	Any time	Prior
Before 1st self-injection with ZLP-AI	After 1st self-injection with ZLP-AI	Baseline (= prior and concomitant)
Any time	After 1st self-injection with ZLP-AI	Concomitant
After 1st self-injection with ZLP-AI	After 1st self-injection with ZLP-AI	Concomitant Only

Where a medication start date is partially or fully missing, and it is unclear as to whether the medication is prior or taken at baseline, it will be assumed that it is taken at Baseline.

Past, Prior, Baseline, Concomitant or Concomitant Only medications will be summarized in the SS. Medications will be presented in alphabetical order by Anatomical Main Group (ATC Level 1), then by Pharmacological Subgroup (ATC level 3) and finally by decreasing frequency of PT.

In the case of ties, sort these alphabetically. Summaries will include the overall number and percentage of participants receiving at least one treatment of a PT.

Medications classified as past, prior, baseline, concomitant or concomitant will be listed using the SS.

A by-participant listing of prior/concomitant procedures will be provided in SS.

Originally reported dates will be used for listings.

6.6.2 Prior and concomitant medications (non-MG therapy)

A non-MG related medication can be identified by the “indication” value on the Prior and Concomitant Medication eCRF form.

Past, Prior, Baseline, Concomitant or Concomitant Only medications (as defined in Section 6.6.1) will be summarized in SS. Medications will be presented in alphabetical order by Anatomical Main Group (ATC Level 1), then by Pharmacological Subgroup (ATC level 3) and finally by decreasing frequency of PT. In case of ties, these will be sorted alphabetically. Summaries will include the overall number and percentage of participants receiving at least one treatment of a PT.

Medications classified as past, prior, baseline, concomitant or concomitant only will be listed in SS. A by-participant listing of concomitant procedures will also be listed using the SS. Originally reported dates will be used for listings.

A separate by participant listing of Neisseria Meningitis Vaccination and Prophylaxis will be provided in SS.

6.6.3 MG Specific Prior and Concomitant Medications

MG specific medication will be presented separately from the other prior and concomitant medications (for both tables and listings). A MG specific medication will be identified by the “indication” value on the Prior and Concomitant Medication eCRF form. MG specific Past, Prior, Baseline, Concomitant and Concomitant only medications will be summarized on the SS as defined in Section 6.6.1.

Additionally, the number and percentage of participants who are taking one or more of the sets of MG specific medications as presented in the below table (i.e., Groups A-H) will be summarized separately for the prior medications and for the baseline medications.

Table 6–2: Medication Classes

Group	Medication Class	Included Text in the Preferred Term based on the Prior/Concomitant eCRF form
A	Corticosteroids	PREDNISONE DEXAMETHASONE METHYLPREDNISONE SODIUM SUCCINATE PREDNISOLONE METHYLPREDNISOLONE HYDROCORTISONE TBD**

Table 6–2: Medication Classes

Group	Medication Class	Included Text in the Preferred Term based on the Prior/Concomitant eCRF form
B	Immunosuppressants	AZATHIOPRINE MYCOPHENOLATE MOFETIL MYCOPHENOLATE ACID
C	Immunoglobulins	Intravenous Immunoglobulin Subcutaneous Immunoglobulin
D	Plasma Exchange or Plasmapheresis ^a	Plasma Exchange Plasmapheresis
E	Immunosuppressants	Cyclosporine Cyclophosphamide Methotrexate Tacrolimus Rituximab TBD ^b
F	Cholinesterase inhibitors	GALANTAMINE PYRIDOSTIGMINE AMBENONIUM NEOSTIGMINE DISTIGMINE
G	FcRn	EEGARTIGIMOD ROZANOLIXIZUMAB
H	C5 inhibitors	ECULIZUMAB RAVULIZUMAB

^a As captured at the procedures eCRF form

^b To be defined: a complete list of corresponding medications and preferred terms will be provided by UCB prior to database lock

6.7 Appendix 7: Data derivation rules

6.7.1 SIAQ version 2.1

The Self-Injection Assessment Questionnaire (SIAQ) version 2.1 is a self-administered Patient-Reported Outcome, which will be administered at Visit 1 and Visit 8 to assess the participants' self-injection experience, including the perceived advantages and the potential limitations of self-injection of a sc medication.

The pre injection SIAQ (SIAQ PRE module) is composed of 7 items with a Likert-type scale of 1 to 5 or 6. The 7 items are grouped into 3 domains (FL: feelings about injection, CO: self-confidence, and SA: satisfaction with the current mode of administration).

The post injection SIAQ (SIAQ POST module) is composed of 21 items with a Likert-type scale of 1 to 5 grouped into 6 domains (FL: feelings about injection, SI: self-image, CO: self-confidence, RE injection site reactions, EU ease of use, and SA: satisfaction with self-injection).

Each domain score of both pre- and post-modules range from 0 to 10, where higher scores indicate a more positive self-injection experience.

The scoring of domains is performed in 2 steps:

- The raw item scores ranging from 1 to 5 (or 1 to 6) are transformed into scores ranging from 0 (worse experience) to 10 (best experience).
- The transformed scores for items contributing to a domain are then averaged into a domain score.

Table 6–3: SIAQ version 2.1: Pre module domain: Scoring of domains from raw item scores

Domain	Items	Transformed item score	Domain score calculation	Domain score range
FL	1-3	$((\text{raw score})-1)*2.5$	Average of transformed item scores	0-10
CO	4-6	$((\text{raw score})-1)*2.5$		
SA	7	$((\text{raw score})-1)*2.5$		

Table 6–4: SIAQ version 2.1: Post module domain: Scoring of domains from raw item scores

Domain	Items	Transformed item score	Domain score calculation	Domain score range
FL	1-3	$((\text{raw score})-1)*2.5$	Average of transformed item scores	0-10
IM	4	$((\text{raw score})-1)*2.5$		
CO	5-7	$((\text{raw score})-1)*2.5$		
RE	8-9	$((\text{raw score})-1)*2.5$		
EU	10-14	$((\text{raw score})-1)*2.0$		
SA	15-21	$((\text{raw score})-1)*2.5$		

In case of missing values, no domain score will be calculated if more than 50% of the items within the domain are missing.

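### SAP 6.7.1 contradicts itself on which SIAQ items have six response levels, so the text and the scoring tables together do not give the stated 0 to 10 range

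*SAP*

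**What the plan says.** SAP Section 4.4.1 sends the reader to Section 6.7.1 for the SIAQ scoring algorithm. On response levels, the text of 6.7.1 says:

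- The pre-injection module "is composed of 7 items with a Likert-type scale of 1 to 5 or 6". It does not say which items have six levels.
- The post-injection module "is composed of 21 items with a Likert-type scale of 1 to 5 grouped into 6 domains". No exception is made for ease of use.

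Each raw item, whether it has five or six levels, is to be rescaled to run from 0 (worst) to 10 (best). Then "The transformed scores for items contributing to a domain are then averaged into a domain score". The result is stated as: "Each domain score of both pre- and post-modules range from 0 to 10, where higher scores indicate a more positive self-injection experience". Protocol Section 8.1.3 gives the same range.

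The multipliers are in two tables:

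- Table 6-3 (pre-injection): (raw − 1) × 2.5 for all seven items.
- Table 6-4 (post-injection): (raw − 1) × 2.0 for ease of use (items 10 to 14), and (raw − 1) × 2.5 for the other 16 items.

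Both tables give 0 to 10 as the domain range.

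**The concern.** A multiplier of 2.5 maps a 1-to-5 item onto 0 to 10, and a multiplier of 2.0 does so for a 1-to-6 item. The text puts the six-level scale in the pre-injection module, whereas the tables put it in post-injection ease of use. Both cannot be right, and a programmer has no other scoring rule in the SAP to turn to.

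SIAQ domain scores are a listed endpoint, and the post-injection scores are also plotted by visit. If the wrong side is followed, the best possible ease-of-use score would appear as 8 beside domains that reach 10, on the domain closest to the handling of a new injector. Alternatively, pre-injection scores above the top of the scale could be reported.

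**Working it through.** **Inputs.** Response levels come from the text of SAP 6.7.1, and multipliers and item groupings from Tables 6-3 and 6-4. Transformed item = (raw − 1) × multiplier; domain = mean of its items. Domain maxima below assume all items are answered.

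**Item counts.** Pre-injection: 3 + 3 + 1 = 7. Post-injection: 3 + 1 + 3 + 2 + 5 + 7 = 21. Both agree with the text, so the tables do not appear to have lost rows.

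**Stated range of 0 to 10.** The lowest raw score always gives (1 − 1) × multiplier = 0. The highest gives:

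| Levels | Multiplier | Maximum |
|---|---|---|
| 5 | 2.5 | (5 − 1) × 2.5 = 10.0 |
| 6 | 2.0 | (6 − 1) × 2.0 = 10.0 |
| 5 | 2.0 | (5 − 1) × 2.0 = 8.0 |
| 6 | 2.5 | (6 − 1) × 2.5 = 12.5 |

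The range reproduces for the five post-injection domains other than ease of use (five levels, 2.5). It fails for the other two pairings of text and table:

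- *Ease of use, five levels, 2.0:* every item has maximum 8.0, so the domain maximum is 8.0. At each raw value above 1 the score is 2.0/2.5 = 0.80 of its proper value, or 20% low.
- *A six-level pre-injection item, 2.5:* the maximum is 12.5. At each raw value above 1 the score is 2.5/2.0 = 1.25 of its proper value, or 25% high.

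**Pre-injection domain maxima.** Satisfaction is the single item 7, so it reaches 12.5 if that item has six levels. For feelings or self-confidence (three items each):

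- one six-level item: (12.5 + 10 + 10)/3 = 10.83
- two: (12.5 + 12.5 + 10)/3 = 11.67
- three: 12.5

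**What the questionnaire might really contain.** Applying the tables as printed:

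| Pre-injection items | Ease-of-use items | Pre-injection domain maximum | Ease-of-use maximum | What is wrong |
|---|---|---|---|---|
| all 5-level | 6-level | 10 | 10 | text only |
| some 6-level | 5-level | 10.83 to 12.5 where affected | 8 | multipliers only |
| all 5-level | 5-level | 10 | 8 | pre-injection text; ease-of-use multiplier |
| some 6-level | 6-level | 10.83 to 12.5 where affected | 10 | post-injection text; pre-injection multiplier |

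**Can the documents choose between these?** No. Protocol 8.1.3 and SAP 4.4.1 give the range but no response levels, and the SAP amendment table lists no change to 6.7.1.

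**The case against.** The strongest reply is that this is a slip of wording. The tables are the operative rule. A separate multiplier for ease of use alone looks deliberate, and 2.5 and 2.0 are exactly the values that five- and six-level items need. If the words allowing six levels were simply attached to the wrong module, a programmer working from the tables gets correct scores and the numerical error is nil. That is plausible, but the documents do not confirm it. What stands is that the existence of a scoring error cannot be asserted, only that of a contradiction.

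The reply on weight also stands. SIAQ is among the other endpoints and is analysed as exploratory. All analyses are descriptive, and no comparison between domains is planned. Ease of use has the same multiplier at Visits 1 and 8, so an error would rescale both visits alike. Item-level summaries and listings are planned and might expose a wrong range.

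A reader might also infer that some items are scored backwards, because every transform increases with the raw code. The SAP amendment table mentions a deleted summary on a five-level scale of how bothered participants were, which could feed that suspicion. The documents do not support the inference: that text is superseded and gives labels without numeric codes, no current item is shown with code 1 as its best answer, and 6.7.1 states that the transformed scale runs from worst to best. It is a question to ask, not a finding.

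**Conclusion.** The inconsistency is real and is confirmed by direct arithmetic. Taking text and tables together, ease of use is capped at 8.0 (20% low), and a six-level pre-injection item reaches 12.5 (25% high), with a domain maximum of 10.83, 11.67 or 12.5 depending on how many of its items have six levels. These sizes are conditional on the text being right about response levels. If the tables are right, computed scores are correct and only the text is at fault.

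Two stronger readings are tempting and should be resisted. The documents do not show that the ease-of-use mean will be biased, since the effect may be zero. Nor do they show that every pre-injection score can reach 12.5, since the SAP does not identify which items, if any, have six levels. Primary and secondary results are untouched. The point still merits correction, because this is the SAP's only scoring rule for a listed endpoint.

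**What to change.** Before database lock:

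1. Check the number of response levels of each of the 7 pre-injection and 21 post-injection items against the implemented questionnaire and the SIAQ user manual in the SAP's reference list.
2. Correct whichever of the text of 6.7.1 or Tables 6-3 and 6-4 is wrong, and state the levels item by item. Each item should use (raw − 1) × 10/(levels − 1), which is 2.5 per step for five levels and 2.0 for six.
3. Add a program check that every transformed item lies within 0 to 10 before averaging. This catches values that are too high; a cap at 8 stays inside the range, so step 1 is needed to catch that.
4. As a query only, confirm in the same pass that raw codes rise towards the better answer, as the transform assumes.
5. Align the self-image domain code, which is SI in the text and IM in Table 6-4.

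The cost is a short SAP wording change and one line of program checking. No new data are needed.

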6.8 Appendix 8: AEs of Interest

Table 6–5: AEs of Interest selection criteria

No	Event (also included in Title of TFL output)	Selection criteria
1	Infections	TEAEs with SOC="Infections and infestations"
2	Hypersensitivity reactions	SMQ='Hypersensitivity' (narrow scope)

Table 6–5: AEs of Interest selection criteria

3	Anaphylactic reactions	
SMQ= ‘Anaphylactic reaction’ and
 
TEAEs meeting at least one of the following criteria where the different terms (within each sub-category) occur on the same date or on 2 consecutive days, under the condition that the zilucoplan treatment is still ongoing at the first of these 2 days.
 
 • If a participant reports any TEAE which codes to a PT included in Category A, then the event will be flagged as an anaphylactic reaction. • If a participant reports any TEAE which codes to a PT included in Category B AND reports any TEAE which codes to a PT included in Category C, and both TEAEs have the same start date or on 2 consecutive days, then both events will be flagged as anaphylactic reactions. 
If a participant reports any TEAE which codes to a PT included in Category D AND reports (either a TEAE which codes to a PT included in Category B OR a TEAE which codes to a PT included in Category C), and both TEAEs have the same start date or on 2 consecutive days, then both events will be flagged as anaphylactic reactions.

4	Malignancies or unspecified tumours	
TEAEs in: SMQ= “Malignant or unspecified tumours (SMQ)” or “Malignant tumours (SMQ)”
 
Note: the events included in the “Malignant tumours” table will be a subset of the events included in the “Malignant or unspecified tumours” table. While the “Malignant tumours (SMQ)” is most relevant, “Malignant or unspecified tumours (SMQ)” must be reviewed for potential malignancies.

Table 6–6: Anaphylactic Reactions Categories

Category	Preferred Term as per MedDRA version 27.0
A	ANAPHYLACTIC REACTION
	ANAPHYLACTIC SHOCK
	ANAPHYLACTIC TRANSFUSION REACTION
	ANAPHYLACTOID REACTION
	ANAPHYLACTOID SHOCK
	CIRCULATORY COLLAPSE

Table 6–6: Anaphylactic Reactions Categories

Category	Preferred Term as per MedDRA version 27.0
	DIALYSIS MEMBRANE REACTION
	KOUNIS SYNDROME
	PROCEDURALSHOCK
	SHOCK
	SHOCK SYMPTOM
	TYPE 1 HYPERSENSITIVITY
B	ACUTE RESPIRATORY FAILURE
	ASTHMA
	BRONCHIAL OEDEMA
	BRONCHOSPASM
	CARDIO-RESPIRATORY DISTRESS
	CHEST DISCOMFORT
	CHOKING
	CHOKING SENSATION
	CIRCUMORAL OEDEMA
	COUGH
	COUGH VARIANT ASTHMA
	CYANOSIS
	DYSPNOEA
	ENHANCED RESPIRATORY DISEASE
	HYPERVENTILATION
	IRREGULAR BREATHING
	LARYNGEAL DYSPNOEA
	LARYNGEAL OEDEMA
	LARYNGOSPASM
	LARYNGOTRACHEAL OEDEMA
	MOUTH SWELLING
	NASAL OBSTRUCTION
	OEDEMA MOUTH
	OROPHARYNGEAL OEDEMA
	OROPHARYNGEAL SPASM
	OROPHARYNGEAL SWELLING
	PHARYNGEAL OEDEMA
	PHARYNGEAL SWELLING
	RESPIRATORY ARREST
	RESPIRATORY DISTRESS
	RESPIRATORY FAILURE
	REVERSIBLE AIRWAYS OBSTRUCTION

Table 6–6: Anaphylactic Reactions Categories

Category	Preferred Term as per MedDRA version 27.0
	SENSATION OF FOREIGN BODY
	SNEEZING
	STRIDOR
	SWOLLEN TONGUE
	TACHYPNOEA
	THROAT TIGHTNESS
	TONGUE OEDEMA
	TRACHEAL OBSTRUCTION
	TRACHEAL OEDEMA
	UPPER AIRWAY OBSTRUCTION
	WHEEZING
C	ALLERGIC OEDEMA
	ANGIOEDEMA
	CIRCUMORAL SWELLING
	ERYTHEMA
	EYE OEDEMA
	EYE PRURITUS
	EYE SWELLING
	EYELID OEDEMA
	FACE OEDEMA
	FLUSHING
	INJECTION SITE URTICARIA
	LIP OEDEMA
	LIP SWELLING
	NODULAR RASH
	OCULAR HYPERAEMIA
	OEDEMA
	OEDEMA BLISTER
	PERIORBITAL OEDEMA
	PERIORBITAL SWELLING
	PRURITUS
	PRURITUS ALLERGIC
	RASH
	RASH ERYTHEMATOUS
	RASH PRURITIC
	SKIN SWELLING
	SWELLING
	SWELLING FACE

Table 6–6: Anaphylactic Reactions Categories

Category	Preferred Term as per MedDRA version 27.0
D	SWELLING OF EYELID
	URTICARIA
	URTICARIA PAPULAR
	BLOOD PRESSURE DECREASED
	BLOOD PRESSURE DIASTOLIC DECREASED
	BLOOD PRESSURE SYSTOLIC DECREASED
	CARDIAC ARREST
	CARDIO-RESPIRATORY ARREST
	CARDIOVASCULAR INSUFFICIENCY
	DIASTOLIC HYPOTENSION
	HYPOTENSION
	HYPOTENSIVE CRISIS
	POST PROCEDURAL HYPOTENSION

